
Specific Aim 1. To conduct a clinical study with aggressive treatment for lower respiratory symptoms in the WTC EHC in order to identify a group of patients with controlled lower respiratory symptoms (CLRS) and a group of patients with persistent uncontrolled lower respiratory symptoms (ULRS).

SA1.a To test whether a three month treatment with combined high dose inhaled corticosteroids (ICS) and long acting bronchodilators (LABA) results in improved lower respiratory symptoms in patients overall.

Specific Aim 2. To test the hypothesis that discrete measures of lung physiology are associated with the status of ULRS and CLRS in patients in the WTC EHC.

SA2.a To test whether bronchial hyperresponsiveness (BHR) is associated with the status of ULRS and CLRS by comparing rates of BHR in patients with ULRS and CLRS.

SA2.b To test whether measurements of airflow and lung volume (FEV₁, FVC, FEV₁/FVC, RV/TLC) and of small airway dysfunction (impulse oscillometry) are associated with ULRS and CLRS status.

Specific Aim 3. To test the hypothesis that inflammatory markers associated with airway disease are increased in patients with ULRS compared to CLRS in the WTC EHC.

SA3.a Compare levels of an exhaled marker of inflammation (Fractional exhaled nitric oxide; FeNO) in patients with ULRS and CLRS.

SA3.b Compare levels of circulating biomarkers associated with a Th2 inflammatory response (total and allergen-specific IgE, circulating eosinophils, C-reactive protein, serum periostin) in patients with ULRS and CLRS.

Specific Aim 4. To test the hypothesis that increased rates of co-morbid conditions are associated ULRS compared to CLRS in the WTC EHC.

SA4.a Compare quantitative measures of PTSD, anxiety or depression in patients with ULRS and CLRS.

SA4.b Compare rates of chronic rhinosinusitis symptoms and probable paradoxical vocal cord motion (PVCM) in patients with ULRS and CLRS.

SA4.c Compare rates of gastroesophageal reflux symptoms in patients with ULRS and CLRS.

Background

Exposure to WTC dust/fumes/gas in the “Survivor” population

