We will enroll patients from our adult clinic which includes patients ≥ 18 years of age (NIH definition of children is < 21) and will include patients up to age 75. Above age 75, there are few normal values for lung function testing.

Racial and Ethnic Origin

We will enroll subjects with the race/ethnic distribution of the data from our monitoring results in the WTC EHC clinic, which is approximately 40% Hispanic, 20% Black, 6% Asian.

Inclusion Criteria

Age ≥ 18 years and <75

Meet criteria for WTC EHC enrollment

Onset of LRS after 9/11/01

Persistent LRS at chart review of WTC EHC Monitoring visit

Pre-bd FEV1 within normal limits at chart review of WTC EHC Monitoring Visit

≤ 5 p-y tobacco

Not current smoker

Asthma Control Test Score ≤ 19 at chart review of WTC EHC Monitoring Visit

Normal CXR

Exclusion Criteria

Age < 18 years and Age ≥75
LRS or asthma history pre 9/11/01
No persistent LRS
pre-bd FEV1 below the lower limit of normal (NHANES)
> 5 p-y tobacco
Current smoker
Asthma Control Test Score ≥20

Abnormal CXR or parenchymal changes on HRCT

Uncontrolled major chronic illness (DM, CHR, cancer, mental health)

History of significant non-WTC occupational or environmental exposure

Allergy to study drug

Pregnancy, lactation or plans to become pregnant

Chronic oral corticosteroids

High risk of fatal or near-fatal asthma within previous 2 years

Other lung disease (IPF, sarcoid etc.)

Vulnerable Subjects

N/A

Methods & Procedures

Methods & Procedures

SA1.a To test whether a three month treatment with combined high dose inhaled corticosteroids (ICS) and long acting bronchodilators (LABA) results in improved LRS.

Trial Scheme. Subject recruitment and a trial scheme visit schedule is shown in Fig 1.

Database Pre-screening. Pre-screening will be used for initial subject recruitment. [name] is a member of the WTC EHC Data Center, and will work in collaboration with the WTC EHC Data Center (collaboration letter included). Only patients who have agreed to be re-contacted will be included. Information on symptom frequency will be obtained from data from the standardized “monitoring” visit. Patients with persistent LRS will be invited for an Initial Visit (V1).

Definition of persistent LRS. We define “persistent LRS” based on definitions for the NIH asthma guidelines as LRS that occurs >

[Fig. 1. Trial visit scheme.](#)

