2x/week in the month preceding the monitoring visit. LRS will include: wheeze, shortness of breath at rest or with mild exertion, or chest tightness. These criteria for inclusion will be confirmed during V1 with a repeat questionnaire.

Sampling strategy for screening and enrollment in V1. Patients will be recruited from the WTC EHC population using block stratification *a priori* to obtain a representative sampling of the monitoring population (i.e. 5 patients with recent monitoring visits, 5 patients with monitoring visits > 1 year previously). The sampling will not be stratified by race/ethnicity, age, and exposure but these variables will be adjusted in statistical analyses. We anticipate that we will telephone 300 patients for our final enrollment of 200 patients for the study.

Inclusion/Exclusion criteria. Detailed inclusion/exclusion criteria for subject identification for potential

enrollment include:

- Onset of LRS after 9/11/01
- Presence of LRS > 2x/week in the month preceding the monitoring visit at chart review of the WTC EHC Monitoring visit **and confirmed in V1**
- Absence of abnormal CXR or other lung disease
- ACT score ≤ 19 at monitoring visit

Detailed exclusion criteria for potential enrollment include:

- Presence of abnormal CXR
- Presence of other lung disease (e.g. ILD, sarcoidosis)
- Current or ≥ 5 p-y tobacco use
- ACT score ≥ 20 at monitoring visit

A study scheme and procedure chart is shown:

Telephone screening visit (SV)

Patients with persistent LRS will be identified from the WTC EHC data base and will be contacted by telephone or in person. Study will be described and interest in study will also be determined.

Enrollment visit (V1)

Control status will be assessed with the Asthma Control Test (ACT), a symptom-based validated instrument^{76, 77}. Questionnaires to assess detailed specific respiratory symptom frequency, current environmental exposures, and severity and co-morbid conditions of PTSD/depression/anxiety will be administered. The Modified Medical Research Council (MMRC) dyspnea scale will be completed to assess degree of dyspnea. Baseline FeNO (fractionated exhaled Nitric Oxide) and pre and post bronchodilator (bd; 360 mcg albuterol) spirometry and IOS will be obtained.

Patients will be treated in the following manner based on assessment at V1:

- Patients who have uncontrolled LRS (ACT < 20) at time of this visit will be provided with study Advair for a total of 3 months.

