	Screening	V1 (enrollment)	V2	V3	V4
Time (weeks)		1	4	8	12
Consent		X			
Inclusion/exclusion	X	X			
Study review	X	X			
ACT		X	X	x	X
Physical Exam		X			
FeNO		X			X
Spirometry (pre/post bd)		X			X
IOS (pre/post bd)		X			X
Adherence counseling		X	X	X	
Daily diary review		X	X	X	
Medication distribution		X	X	X	
Classification confirmation		X			X
Co-morbid Medical Questionnaire (GSAS,SSS)			X		
Vocal Handicap Index					X
Respiratory questionnaire (ASUI)		X			X
Mental Health Questionnaires (SF12V2, PHQ, PCL)		x			x
MMRC Dyspnea Scale		X			X
VCD assessment					X
MCT				X	
Pregnancy test		X		X	
Blood		X			
AE screen			X	X	X
Leicester Cough Questionnaire				X	
Urine Sample for Cotinine				X	
6 minute walk test				x	

- Patients who have uncontrolled LRS at V1, but do not fit criteria for Step 3,4 or 5 asthma therapy according to NIH EPR III asthma guidelines will be deferred from the study until they have been seen by their physician and tried on ICS therapy.
- Patients who had symptoms at monitoring visit but are now controlled at V1 will be asked to continue their current treatment (or no treatment) and will continue with the study. They will not be provided with any medications.

Study medication will be provided as open label high dose ICS/LABA diskus (fluticasone /salmeterol; 500/50 mcg; 1 inhalation twice daily, or MDI 230/21, 2 puffs bid) for a 1 month period. Inhaler training and adherence counseling will be performed. Patients will be instructed to maintain a daily diary.

Adherence visit (V2) Patients will return for a monthly visit. At this visit the study will be reviewed, inhaler technique reviewed, and adherence counseling administered. Notation of the counter denoting actuation of the ICS/LABA diskus will be made to assess adherence. Daily diary will be reviewed. Patients will be queried for any adverse effects. Questionnaires to assess co-morbid conditions of chronic rhinosinusitis, and gastroesophageal reflux (GER) will be administered as well as the ACT to assess for control status

Adherence visit (V3) This visit will be similar to V2, however, a methacholine challenge test with lung volumes and oscillometry will also be performed on all patients. Patients will complete the Leicester Cough Questionnaire at Visit 3. Urine will be obtained for cotinine measurements. as well as the ACT to assess for control status

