Sample size estimation

Our primary outcome will be the rate of LRS and CLRS after the 3 month adherence period (SA1). We base our sample size and recruitment on our initial analysis of the WTC EHC monitoring in which 88% of patients who had ever received ICS or ICS/LABA had an ACT score of ≤ 19 . We assume however, that many of these patients were either no longer using medication at the time of the assessment, were on minimal dose, or were non-adherent. Thus we predict by V4 that we will have a 60% rate of ULRS and a total of 200 patients would yield 120 patients who will fit criteria as ULRS and 80 as CLRS. To take into account potential screen failures and dropouts, we will approach 300 patients initially to obtain the total sample size of 200. We will include drop-outs in our intention to treat analysis as these patients can be considered for baseline analysis.

For categorical endpoints, such as BHR, PTSD and PVDMM, the sample sizes of 120 in ULRS group and 80 in CLRS group will achieve 80% power to detect an odds ratio of 2.08 at significance level of 0.05, assuming that the rate of disease is 30% in the CLRS group. A logistic regression of the ULRS vs. CLRS on a continuous,

normally distributed variable (such as depression score or log-FeNo) with a sample size of 200 observations will achieve 80% power at a 0.05 significance level to detect an OR of 1.498 for 1- standard deviation (SD) difference in the continuous covariate.

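### SA1.a is worded as a causal test of high-dose ICS/LABA, but the stated primary outcome has no contrast, pools treated with untreated patients, and cannot isolate a drug effect

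*Combined protocol and SAP*

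**What the plan says.** Under Specific Aim 1, SA1.a is a test of whether the three-month regimen "results in improved lower respiratory symptoms in patients overall". The Methods section restates it in nearly the same terms.

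Patients are selected on the outcome scale twice. The Inclusion Criteria require "Asthma Control Test Score ≤ 19 at chart review of WTC EHC Monitoring Visit". Then, under Enrollment visit (V1), "Patients who have uncontrolled LRS (ACT < 20) at time of this visit will be provided with study Advair". Uncontrolled patients who do not meet the guideline-step criteria are deferred. Patients found controlled at V1 "will be asked to continue their current treatment (or no treatment) and will continue with the study", and "They will not be provided with any medications".

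The drug is not blinded: "Study medication will be provided as open label high dose ICS/LABA diskus". It comes with inhaler training, adherence counselling, a diary and monthly visits. No randomised or concurrent control group is described.

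Under Control Classification, ULRS or CLRS status rests on the V4 ACT alone. Sample size estimation states: "Our primary outcome will be the rate of LRS and CLRS after the 3 month adherence period (SA1"; the first term is evidently ULRS. It predicts 60% ULRS, and gives 88% with ACT of 19 or less among patients who had ever received ICS or ICS/LABA. The section on statistical analysis describes comparisons and logistic models of ULRS against CLRS. It gives no analysis of change from V1 to V4 and no test for SA1.a.

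**The concern.** The aim makes a causal claim about a drug, and the outcome attached to it is a single proportion at one visit. Three features stand between the two.

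- **No contrast.** No null rate, baseline comparison or control rate is declared. The 88% is a planning figure. The protocol itself expects that many of those patients were off medication, on a minimal dose or non-adherent.
- **Mixed population.** The V4 rate covers all enrolled patients, including those controlled at V1 who never receive study drug. An untreated patient who is controlled at V1 and at V4 counts towards the expected 80 CLRS.
- **Selection in the treated group.** All treated patients have ACT below 20 at V1. On the controlled/uncontrolled scale they have nowhere to go but up, and some will cross the cut on re-measurement with no drug effect.

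The Innovation section hopes that the findings will guide therapy, including a later reduction in corticosteroids. A causal benefit of high-dose ICS/LABA read from this rate would therefore carry weight that the design cannot give it.

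**Working it through.** **1. The plan's own figure.** With N = 200 and 60% ULRS (Sample size estimation), 200 × 0.60 = 120 and 200 × 0.40 = 80. The split reproduces. The 95% half-width is 1.96 × √(0.60 × 0.40 / 200) = 0.068, so the primary outcome is a descriptive rate of 60% ± 6.8 points. Both power statements in that section concern ULRS against CLRS, not SA1.a.

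**2. What pooling does.** Let c be the share of the 200 who are controlled at V1, untreated, and still controlled at V4. The documents do not give c. The CLRS rate among treated patients is then (80 − 200c) / (200 − 200c).

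| c | Treated | CLRS among treated | Rate |
|---|---|---|---|
| 0% | 200 | 80 | 40% |
| 10% | 180 | 60 | 33% |
| 20% | 160 | 40 | 25% |
| 30% | 140 | 20 | 14% |
| 40% | 120 | 0 | 0% |

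The same predicted 60% ULRS is thus compatible with anything from 40% to none of the treated patients being controlled.

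**3. Regression to the mean with zero drug effect.** Assumptions: ACT is treated as a normal score with the same distribution at the monitoring visit, V1 and V4; correlation r is equal between any two visits; a share U of the source population lies below the cut. U = 88% is the protocol's figure for ever-users of ICS or ICS/LABA. U = 70% and 60%, and r = 0.5-0.8, are assumptions. With P2 the probability that two scores are below the cut and P3 that all three are, the share of treated patients controlled at V4 is 1 − P3/P2. For U = 88% and r = 0.5: 1 − 0.745/0.802 = 7.1%.

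| U | r = 0.5 | 0.6 | 0.7 | 0.8 |
|---|---|---|---|---|
| 88% | 7% | 6% | 5% | 4% |
| 70% | 16% | 13% | 11% | 8% |
| 60% | 20% | 17% | 14% | 10% |

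This gives about 4-7% on the protocol's figure and 8-20% if 60-70% were below the cut. With U = 88% and a stationary distribution, even r = 0 gives only 12%.

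**4. Effect on a before/after test.** The plan names none, so these are illustrations.

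- *McNemar on control status.* Changes can go in one direction only. Six improvers give two-sided p = 2 × 0.5⁶ = 0.031. At a 5% no-effect rate, six or more improvers occur with binomial probability 0.56 for n = 120 and 0.94 for n = 200.
- *Paired test on the ACT score*, selection at V1 only, U = 88%. The cut is t = 1.175 SD and λ = φ(t)/U = 0.227. The spurious shift is (1 − r)λ, which is 0.114 SD at r = 0.5 and 0.023 SD at r = 0.9. The false-positive rate at a nominal 5% runs from 9% (r = 0.9, n = 120) to 39% (r = 0.5, n = 200).

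**5. Can the monitoring-visit-to-V1 change serve as a gauge of re-measurement?** Not in treated patients. They are below the same cut at both visits, and under equal correlation the two scores are exchangeable, so the expected change is zero whatever the size of the regression effect. The no-effect V1-to-V4 change in the same patients is 0.03-0.09 SD for U = 88% (r = 0.8-0.5) and reaches 0.25 SD for U = 60%, r = 0.5. The gauge would falsely reassure.

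**The case against.** The strongest defence is that Aim 1 exists to sort patients into ULRS and CLRS, that the overall hypothesis concerns correlates of ULRS, and that all stated power serves those comparisons. Counselling is deliberate, since poor adherence is one of the protocol's named explanations for uncontrolled symptoms. This stands for the parent aim: forming the groups for SA2-SA4 needs no control arm. It does not cover SA1.a, which is written as a test of what treatment brings about.

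A reader might also infer stronger things that the documents do not support:

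- *That SA1.a must come out positive.* No success criterion is stated, a mean ACT score can fall, and the illustrations in steps 4's two tests give inflated probabilities, not certainty.
- *That the predicted fall to 60% ULRS is an artefact of selection.* Under the assumptions above, regression yields at most about 20% controlled among the treated, and 4-7% on the protocol's own figure, against the 40% CLRS predicted for the whole sample.
- *That 88% against 60% is the intended test.* It is not declared as one. The 88% comes from patients who had ever received ICS or ICS/LABA, not from the enrolled patients at V1.
- *That V1-controlled patients provide a control group.* They are untreated, but they are defined by the baseline value of the outcome, so they are not comparable with the treated.

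**Conclusion.** The concern holds for SA1.a and for the interpretation of the primary outcome, and no further. The V4 rate has no contrast and mixes treated with untreated patients. Within the treated group, selection at V1 makes control status a one-way outcome. Drug effect cannot be separated from regression to the mean, open-label reporting, counselling and repeated visits.

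Only the regression component can be sized, and it is modest: the 4-7% and 8-20% in step 3. These figures rest on a stationary normal score, an assumed correlation and, for the higher range, an assumed share below the cut. The other components come on top, and the documents give no basis for sizing them. This should be corrected before analysis, but it does not threaten SA2-SA4.

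**What to change.** 1. Define the SA1.a population as patients given study drug at V1.
2. In that population, report the within-patient V1-to-V4 change in ACT and the V4 control rate, each with a 95% CI.
3. Report the V4 control rate of V1-controlled, untreated patients separately, and not as a comparator.
4. Reword SA1.a and its conclusion as change during three months of supervised treatment, not as an effect of the drug.
5. Do not use the monitoring-visit-to-V1 change in treated patients as a check on re-measurement, for the reason in step 5 of the working.

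The cost is some wording and a short analysis paragraph. ACT is already scheduled at V1 to V4, so no visits, patients or changes to care are needed. The price is a more modest claim. Keeping the causal claim would require a concurrent comparator, which is a different study.

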Classification visit (V4): After 3 months, patients will return for their Classification. At this visit, medication use will be reviewed by noting the medication actuations, and ACT and disease-specific questionnaires for asthma control (ASUI) will be completed^{78, 79}. Screening instruments for post-traumatic stress disorder (PTSD), depression and anxiety will be completed. Blood will be obtained for total and allergen specific IgE, peripheral eosinophil measurements, and measurements of serum periostin and C-reactive protein. FeNO, pre and post BD spirometry and IOS will be performed. Patients will complete a 6 minute walk test. Patients will also undergo laryngoscopy and vocal cord assessment. If patients are unable to complete the vocal cord assessment on the same day as V4, they will be asked to return for a separate visit within two weeks of the end of study (Day 76-90) and will be compensated \$100 for this additional time and effort.

Control Classification. Patients will be classified as ULRS or CLRS based on the ACT score obtained at V4.

Specific Aim 2. To test the hypothesis that discrete measures of lung physiology are associated with patients in the WTC EHC with ULRS compared to CLRS.

Preliminary data pertinent for SA2.

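### The V4 ULRS/CLRS rate pools patients given no study ICS/LABA, so it cannot answer SA1.a, and no analysis of the treated patients is planned; SA2.a is open to confounding by V1 status

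*Combined protocol and SAP*

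**What the plan says.** All references are to the combined protocol and SAP.

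- **Aim.** Specific Aim 1 is "To conduct a clinical study with aggressive treatment for lower respiratory symptoms in the WTC EHC", in order to sort patients into a controlled and an uncontrolled group. SA1.a then asks whether three months of high-dose ICS/LABA "results in improved lower respiratory symptoms in patients overall".
- **Who is treated.** The section on the enrollment visit states: "Patients who have uncontrolled LRS (ACT < 20) at time of this visit will be provided with study Advair for a total of 3 months". Of the others, the list after the visit chart says "Patients who had symptoms at monitoring visit but are now controlled at V1 will be asked to continue their current treatment (or no treatment", that they carry on in the study, and "They will not be provided with any medications". A third group, uncontrolled but not meeting the guideline treatment step, is deferred.
- **Classification.** Control Classification: "Patients will be classified as ULRS or CLRS based on the ACT score obtained at V4". V1 status and study treatment play no part.
- **Primary outcome.** Sample size estimation: "Our primary outcome will be the rate of LRS and CLRS after the 3 month adherence period (SA1", and "Thus we predict by V4 that we will have a 60% rate of ULRS", projected on all 200 patients as 120 ULRS and 80 CLRS.
- **Analysis.** Statistical analysis of the data describes only ULRS versus CLRS comparisons. Age, gender, BMI and WTC exposures are given as examples of adjustment variables. V1 control and receipt of study drug are not named.
- **Methacholine test.** The BHR text under SA2.a describes every patient as having had two months of study therapy by V3, and notes that ICS can lower BHR.

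**The concern.** SA1.a is a question about a treatment. Patients who never receive the study drug carry no information on what it does, yet they enter the only rate the plan defines for V4. By selection they are controlled at the start, so they are likely to be uncontrolled at V4 less often than the treated patients. The pooled rate would then show more control than was seen after study treatment. The analysis section provides no treated-only rate and no V1-to-V4 change, so nothing else fills the gap.

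The same mixing reaches SA2.a. Patients controlled at V1 may gather in the CLRS group at V4, and at the methacholine test they differ from the rest in both disease course and study treatment. The BHR text assumes uniform treatment at that point, which the V1 rules contradict.

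**Working it through.** **1. The plan's own figure.** 200 × 0.60 = 120 ULRS and 200 − 120 = 80 CLRS. This reproduces. The plan does not say whether 60% is expected over everyone or after study treatment. It is projected on all 200, but the supporting argument concerns patients off medication, on minimal dose or non-adherent. Both readings are therefore worked.

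**2. Inputs that the documents do not give (assumptions).** Let s be the share of the 200 controlled at V1, taken as 10–30%, and k the share of those still controlled at V4, taken as 70–90%. The true s may be zero.

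**3. Formulas.**
- If 60% is the pooled rate: treated rate = (0.60 − s(1 − k)) / (1 − s).
- If 60% is the treated rate: pooled rate = 0.60(1 − s) + s(1 − k).

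Example with s = 0.2, k = 0.8: (0.60 − 0.04)/0.8 = 0.70, and 0.48 + 0.04 = 0.52.

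| s | Treated ULRS rate if pooled is 60% (k = 70/80/90%) | Pooled ULRS rate if treated is 60% (k = 70/80/90%) |
|---|---|---|
| 10% | 63.3 / 64.4 / 65.6% | 57 / 56 / 55% |
| 20% | 67.5 / 70.0 / 72.5% | 54 / 52 / 50% |
| 30% | 72.9 / 77.1 / 81.4% | 51 / 48 / 45% |

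The same pooled 60% fits treated rates from 63% to 81%, and 60% itself if s = 0. In the last column the 120/80 split would become 90–114 ULRS and 86–110 CLRS (200 × 0.45 to 200 × 0.57).

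**4. Make-up of the CLRS group.** With a pooled rate of 60%, the share of CLRS patients who never had study drug is s × k / 0.40. At s = 0.2 this is 0.14/0.40 = 35% to 0.18/0.40 = 45%.

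**5. Can the direction of any SA2.a bias be fixed?** Take s = 0.3, k = 0.8, a pooled rate of 60%, and no BHR association within either V1 group. V1-controlled patients are then 0.24/0.40 = 60% of CLRS and 0.06/0.60 = 10% of ULRS.
- BHR 20% if controlled at V1, 40% if not: CLRS 0.6 × 0.2 + 0.4 × 0.4 = 0.28; ULRS 0.1 × 0.2 + 0.9 × 0.4 = 0.38; crude OR (0.38/0.62)/(0.28/0.72) = 1.58.
- BHR 50% and 30%: CLRS 0.42; ULRS 0.32; crude OR (0.32/0.68)/(0.42/0.58) = 0.65.
- Equal BHR in both V1 groups: crude OR 1.00.

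Every BHR input here is assumed. The cases show only that the sign is open: lack of study ICS could raise BHR in V1-controlled patients, while milder disease or their own ICS could lower it.

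**6. Texts side by side.** The V1 rules give no study drug to patients controlled at V1; the BHR text gives all patients two months of it by V3. Both cannot hold if any such patient is enrolled. Separately, the eligibility text has persistent symptoms (more than twice weekly) re-checked at V1, while the V1 rules keep patients who are controlled by then.

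**The case against.** Several points on the other side have weight.

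- **The primary outcome is tied to SA1, the sorting aim, not to SA1.a.** This stands. The all-patient rate is a proper classification result, and nothing here calls for dropping V1-controlled patients. But SA1.a is then left with no planned analysis. Its reference to patients overall does not help, because some of them do not receive the treatment in question.
- **The group may be empty.** This is possible, since persistent symptoms are re-checked at V1. However, symptom frequency and ACT control are different criteria, and the plan writes a rule for patients controlled at V1, so it expects some.
- **The adjustment list is open.** True; V1 status could be added, but nothing commits the analyst to it.
- **SA2.a is associational.** This stands. Whether BHR and V4 status are associated can still be estimated. What is at risk is reading the result as BHR persisting despite study therapy.

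Two stronger readings are tempting. A reader might infer that ACT of 20 or more at V1 makes these patients ineligible, because one line under Exclusion Criteria gives no time point. The detailed list under Methods & Procedures ties that criterion to the monitoring visit, so it is not part of the conflict. A reader might also take the plan's 30% rate and odds ratio of 2.08 as values within treated patients and derive a distorted pooled odds ratio. Sample size estimation states both for the whole CLRS and ULRS groups, so that step relabels the plan's inputs.

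**Conclusion.** The point holds for SA1.a. The pooled V4 rate mixes patients who did and did not receive study ICS/LABA, and no planned analysis isolates those who did. That follows from the text alone. The size does not: the 63–81% and 45–57% ranges rest on the assumed 10–30% share and 70–90% continued control, and the gap vanishes if nobody is controlled at V1.

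For SA2.a the supportable statement is narrower. The comparison is open to confounding by V1 status and study-drug receipt, with direction and size unknown. It is not shown to be confounded, and there would be no such bias if BHR were equal across V1 groups. The contradiction over study therapy at V3 is real and needs correcting whatever the size. This should be fixed, but it does not undermine the classification purpose of the study.

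**What to change.** 1. **SA1.a.** Prespecify the V1-to-V4 change in ACT and the V4 ULRS/CLRS rate in patients with ACT below 20 at V1 who received study ICS/LABA. Show V1-controlled patients separately and keep the all-patient rate as the classification result. State that the treated result is a single-arm before/after comparison. Every treated patient is uncontrolled at V1 by selection, so some apparent improvement from regression to the mean remains.
2. **SA2 and SA3.** Keep the planned ULRS versus CLRS comparisons as the main analyses. Add two sensitivity analyses: one stratified by V1 status/study-drug receipt (for example Mantel-Haenszel for BHR), and one in treated patients only. State three limits. V1 control and study-drug receipt coincide by design, so their effects cannot be separated. V1 ACT is an earlier measure of the outcome, so stratifying may remove part of the association sought; this is why it should not replace the main analysis. Precision is lower.
3. **Text.** Reconcile the V1 treatment rules with the BHR section on what therapy patients have had by V3. Reconcile the V1 re-check of persistent symptoms with keeping patients who are controlled at V1.

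**Cost.** The visit chart already records ACT at V1 and V4 and medication distribution, so no new visit or test is needed. At a 20% share, the treated-only analysis has 160 of 200 patients. With the same ULRS/CLRS split and BHR rates, standard errors grow by a factor of √(200/160) = 1.12. V1-controlled ULRS patients would number only 200 × 0.2 × (0.1 to 0.3) = 4 to 12, so an odds ratio within that group would be descriptive. These patients' own ICS use may be incompletely recorded, since medication use at V4 is reviewed through actuation counts.
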